## **8.3 Reporting Procedures**

### **8.3.1 Reporting Serious Adverse Events**

SAEs will be followed until resolution even if this extends beyond the study-reporting period. Resolution of an AE is defined as the return to pretreatment status or stabilization of the condition with the expectation that it will remain chronic.

**Any AE (including MAAEs, NOCMC, and PIMMCs) that is considered an SAE must be submitted immediately (within 24 hours of site awareness) on an SAE form to the DMID Pharmacovigilance Group, at the following address:**

### **8.3.2 Regulatory Reporting for Studies Conducted Under a DMID Sponsored IND**

Following notification from the site PI or appropriate sub-investigator, DMID, as the IND sponsor, will report any suspected unexpected SAE only if there is evidence to suggest a causal relationship between the study intervention and the AE. DMID will submit an IND safety report to the FDA and will notify the site PI of potential serious risks from clinical studies or any other source, as soon as possible. DMID will report to the FDA any unexpected fatal or life-threatening suspected adverse reaction as soon as possible, but in no case later than 7 calendar days after the sponsor's initial receipt of the information. If the event is not fatal or life-threatening the IND safety report will be submitted within 15 calendar days after the sponsor determines that the information qualifies for reporting as specified in 21 CFR Part 312.32. Relevant follow up information to an IND safety report will be submitted as soon as the information is available.

All SAEs designated as "not related" to study product(s), will be reported to the FDA at least annually in a summary format.

---

### **8.3.3 Reporting of Pregnancy**

Pregnancies occurring in study subjects will be reported via Advantage eClinical on the Pregnancy Report form. No further study vaccinations will be administered to pregnant subjects, but with the subject's permission all protocol-required venous blood samples will be obtained and the subject will continue to be followed for safety for the duration of this trial. Efforts will be made to follow all pregnancies reported during the course of this trial to pregnancy outcome pending the subject's permission.

The pregnancy will be documented on the Pregnancy Reporting Form provided by Emmes, and this form will be used for the pregnancy event data entry into Advantage eClinical. All study mandated blood samples will be obtained and the participant will continue in follow-up for safety events. Pregnancies will be followed until 30 days after delivery to determine outcome, including spontaneous or voluntary termination, details of the birth, and the presence or absence of any birth defects, congenital abnormalities, or maternal and/or newborn complications. No subsequent product injections will be administered to pregnant participants.

### **8.3.4 Disclosure of Study Related Information**

Subjects can choose to receive written disclosure of their treatment assignment after the database has been locked.

## **8.4 Type and Duration of Follow-up of Subjects after Adverse Events**

AEs will be assessed and followed from initial recognition of the AE through end of the protocol defined follow-up period.

SAEs will be followed up through resolution even if duration of follow-up goes beyond the protocol-defined follow-up period.

Resolution of an AE is defined as the return to pre-treatment status or stabilization of the condition with the expectation that it will remain chronic.

Follow-up procedures, evaluations, and outcomes will be recorded on the appropriate data collection form.

---

## **8.5 Procedures to be Followed in the Event of Abnormal Laboratory Test Values or Abnormal Clinical Findings**

The site PI or appropriate co-investigator is responsible for reporting all AEs/SAEs that are observed or reported during the study, regardless of the relationship to study product. AEs/SAEs, abnormal clinical laboratory test values, or abnormal clinical findings will be documented, reported and followed appropriately.

Clinical safety laboratory results from specimens obtained after the first study product injection will be graded as indicated in the Toxicity Tables in [Appendix C](#). Clinical laboratory evaluations assessed on the day of and prior to the first study product injection (Day 1) will be considered as baseline.

Systolic and diastolic blood pressures obtained following vaccination will be defined as AEs and graded as indicated in the Toxicity Tables in [Appendix C below](#). However, baseline values prior to the first vaccination, including values obtained at the screening visit and at Visit 1 prior to vaccine administration, may meet the inclusion criteria of systolic blood pressure 85 to 150 mmHg, inclusive, but fall within values defined as Grade 1 severity in the Toxicity Table. Similarly, baseline values may meet the inclusion criteria of diastolic blood pressure  $\leq$  100 mmHg but fall within values defined as Grade 1 severity in the Toxicity Table. For those participants with baseline blood pressure values that are defined as Grade 1 in the Toxicity Table, subsequent, post-vaccination, values will not be defined as an AE unless the post-vaccination value meets the criteria for Grade 2 or 3 and therefore represents a change from baseline. Those values that represent a change from baseline will be defined as Grade 1 AEs for the Grade 2 values and Grade 2 AEs for the Grade 3 values as they represent a change of one two grades from baseline, respectively.

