## 3.3 Study Endpoints or Outcome Measures

### 3.3.1 Primary

- Occurrence of study vaccine-related SAEs from the time of the first study vaccination through approximately 12 months after the last study vaccination.
- Occurrence of solicited injection site and systemic reactogenicity events from the time of each study vaccination through 7 days after each study vaccination.
- Occurrence of clinical safety laboratory AEs from the time of each study vaccination through approximately 28 days after each study vaccination.
- Occurrence of all unsolicited AEs, regardless of the assessment of seriousness or relatedness, from the time of each study vaccination through 28 days after each study vaccination.
- Occurrence of SAEs, MAAEs, NOCMCs, and PIMMCs from the time of the first study vaccination through approximately 12 months after the last study vaccination.

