## 6.2 Visit 01 Day 01, Enrollment and First Study Product Injection, Clinic Visit

Prior to the study product injection, the following procedures will be performed:

- Medical history and concomitant medications will be reviewed.
- A targeted physical examination will be performed by a study clinician licensed to make medical diagnoses and listed on the Form FDA 1572 as the site PI or sub-investigator, if indicated by medical history.
- Vital signs, including oral temperature, blood pressure, and pulse, will be obtained to ensure eligibility and establish baseline. Subjects must not eat or drink anything hot or cold, or smoke, within 10 minutes prior to oral temperature measurement.
- Inclusion/exclusion criteria, including the results of all clinical screening laboratory evaluations, will be reviewed to verify eligibility
- For women of childbearing potential, contraceptive methods will be reviewed to ensure eligibility, recent menstrual history will be obtained, pregnancy avoidance counseling will be provided, and a urine pregnancy test will be performed. A test performed on a sample obtained within 24 hours prior to vaccination must be negative.
- A pre-administration reactogenicity assessment will be performed to establish baseline.
- Venous blood samples will be obtained for safety labs, PBMC isolation, and immunologic assays in volumes as specified in Table 8, for Groups A, B, D, and E, and Table 9 for Group C. The clinical safety laboratory results will not be available or reviewed prior to study vaccination.
- The assigned study product will be administered IM injection in the deltoid muscle of the preferred arm. The site of injection (right or left arm) and time of administration will be recorded on the appropriate eCRF.
- Subjects will be observed in the clinic for at least 30 minutes after the injection. The injection site will be examined, post-administration reactogenicity assessments will be performed, and any AE or SAE will be recorded on the appropriate eCRF prior to discharge from the clinic.
- Subjects will be provided with a web-based electronic Memory Aid (e-Memory Aid) or Paper Memory Aid and thermometer for recording daily maximum oral temperature, solicited injection site and systemic reactions, unsolicited AEs, and concomitant medications, beginning on the evening of Day 1 and continuing daily for the next 7 days. Subjects will be

---

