#### 8.1.1 Adverse Events (AEs)

The International Conference on Harmonisation (ICH) E6 defines an AE as any untoward medical occurrence in a patient or clinical investigation subject administered a pharmaceutical product regardless of its causal relationship to the study treatment. The FDA defines an AE as any untoward medical occurrence associated with the use of a drug in humans, whether or not considered drug related.

An AE can therefore be any unfavorable and unintended sign (including an abnormal laboratory finding), symptom, or disease temporally associated with the use of medicinal (investigational) product. The occurrence of an AE may come to the attention of study personnel during study

---

visits and interviews of a study recipient presenting for medical care, or upon review by a study monitor.

All AEs, including solicited local (injection site) and systemic (subjective and quantitative) reactions, will be captured on the appropriate eCRF. Information to be collected for AEs includes event description, date of onset, assessment of severity, relationship to study product and alternate etiology (assessed only by those with the training and authority to make a diagnosis and listed on the Form FDA 1572 as an investigator), date of resolution, seriousness and outcome. AEs occurring during the trial collection and reporting period will be documented appropriately regardless of relationship. AEs will be followed through resolution.

Any medical condition that is present at the time that the subject is screened will be considered as baseline and not reported as an AE. However, if the severity of any pre-existing medical condition increases, it should be recorded as an AE.

If an event meets both the criteria of a study endpoint and an AE, the event will be reported either as a study endpoint or as an AE (not both).

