4.5.1. Safety Variables

Serious adverse events (SAEs) will be assessed from the time of the first study product injection through the end of the follow-up which is approximately 12 months after the last study product injection.

Solicited adverse events (AEs) will document reactogenicity events occurring from the time of each study product injection through 7 days after each study product injection. Injection site reactions of interest include pruritus, erythema, induration/swelling, pain, and tenderness. Systemic reactions of interest include fever, chills, fatigue malaise, myalgia, arthralgia, headache, nausea, and vomiting.

Unsolicited AEs will document non-serious AEs occurring from the time of each study product injection through 28 days after the study product injection.

Clinical safety laboratory AEs will be collected on the day of and prior to each study product injection, approximately 7 days after each study product injection, and approximately 28 days after each study product injection (which may also serve as the clinical safety laboratory samples for the second and/or third study product injection). Parameters to be evaluated include white blood cells (WBC), hemoglobin, platelets, alanine aminotransferase (ALT), and creatinine.

MAAEs, NOCMCs, and PIMMCs will be assessed from the time of the first study product injection through the end of the follow-up period, which is approximately 12 months after the last study product injection.

All solicited and unsolicited AEs and laboratory values are graded on a scale of 0 (absent), 1 (mild), 2 (moderate), and 3 (severe) according to toxicity grading scales ([Table 6](#), [Table 7](#)).

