Time Point	Treatment Group	N	None		Mild / Grade 1		Moderate/ Grade 2		Severe/ Grade 3		Missing	
			n	%	n	%	n	%	n	%	n	%
Study Day 208	30 µg Sm-p80 + 5 µg GLA-SE (delayed booster)											
Max Severity Post Baseline	100 µg Sm-p80 (unadjuvanted)											
	10 µg Sm-p80 + 5 µg GLA-SE											
	30 µg Sm-p80 + 5 µg GLA-SE (delayed booster)											
	30 µg Sm-p80 + 5 µg GLA-SE											
	100 µg Sm-p80 + 5 µg GLA-SE											

Note: The “Max Post Baseline” rows indicate the maximum severity experienced by each subject at any time point post baseline, including unscheduled assessments.

Note: N = Number of subjects in the Safety Population with lab results at the specified visit.

Tables with similar format to [Table 59](#):**Table 60: Laboratory Results by Parameter, Maximum Severity, Time Point, and Treatment Group – Creatinine****Table 61: Laboratory Results by Parameter, Maximum Severity, Time Point, and Treatment Group -- Alanine Aminotransferase**

Table 62: Abnormal Laboratory Results Related to Study Treatment by Parameter, Maximum Severity, Time Point, and Treatment Group – Any Chemistry Parameter

[Implementation Note: Only scheduled time points at which at least one related abnormal lab result is observed in any treatment group will be shown. Add group name to treatment, e.g. "Group A: 100 µg Sm-p80 (unadjuvanted)".]

Time Point	Treatment Group	N	None			Mild / Grade 1		Moderate/ Grade 2		Severe/ Grade 3	
			n	%	n	%	n	%	n	%	n
Study Day 1 (Baseline)	100 µg Sm-p80 (unadjuvanted)	x	x	x	x	x	x	x	x	x	x
	10 µg Sm-p80 + 5 µg GLA-SE										
	30 µg Sm-p80 + 5 µg GLA-SE (delayed booster)										
	30 µg Sm-p80 + 5 µg GLA-SE										
	100 µg Sm-p80 + 5 µg GLA-SE										
Study Day 8	100 µg Sm-p80 (unadjuvanted)										
	10 µg Sm-p80 + 5 µg GLA-SE										
	30 µg Sm-p80 + 5 µg GLA-SE (delayed booster)										
	30 µg Sm-p80 + 5 µg GLA-SE										
	100 µg Sm-p80 + 5 µg GLA-SE										
Study Day 29	100 µg Sm-p80 (unadjuvanted)										
	10 µg Sm-p80 + 5 µg GLA-SE										
	30 µg Sm-p80 + 5 µg GLA-SE (delayed booster)										
	30 µg Sm-p80 + 5 µg GLA-SE										
	100 µg Sm-p80 + 5 µg GLA-SE										
Study Day 36	100 µg Sm-p80 (unadjuvanted)										
	10 µg Sm-p80 + 5 µg GLA-SE										
	30 µg Sm-p80 + 5 µg GLA-SE (delayed booster)										
	30 µg Sm-p80 + 5 µg GLA-SE										
	100 µg Sm-p80 + 5 µg GLA-SE										

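### The SAP's laboratory summaries cannot separate grades already present on the Day 1 pre-dose draw from grades that arise after dosing

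*Protocol*

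**What the plan says.** Laboratory events are a primary endpoint (Protocol Section 3.3.1): "Occurrence of clinical safety laboratory AEs from the time of each study vaccination through approximately 28 days after each study vaccination".

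Protocol Section 8.5 sets the grading: "Clinical safety laboratory results from specimens obtained after the first study product injection will be graded as indicated in the Toxicity Tables" in Appendix C. It then names the reference draw: "Clinical laboratory evaluations assessed on the day of and prior to the first study product injection (Day 1) will be considered as baseline". It does not say what a graded Day 1 value means for later grades. For blood pressure the same section does say so. A subject with a Grade 1 reading before the first dose is handled as follows: "subsequent, post-vaccination, values will not be defined as an AE unless the post-vaccination value meets the criteria for Grade 2 or 3".

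Screening may take place up to 30 days before the first injection (Protocol Section 6.1). Blood is drawn again on Day 1, but "The clinical safety laboratory results will not be available or reviewed prior to study vaccination" (Protocol Section 6.2).

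The general rule on pre-existing conditions is tied to screening (Protocol Section 8.1.1, repeated in SAP Sections 3.3 and 9): "Any medical condition that is present at the time that the subject is screened will be considered as baseline and not reported as an AE".

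On the analysis side, SAP Section 4.5.1 places pre-dose draws under the laboratory AE heading: "Clinical safety laboratory AEs will be collected on the day of and prior to each study product injection". Tables 59–61 (chemistry) and 67–70 (hematology) show counts by grade at each visit, including Day 1, and a maximum row. The footnote says of that row: "rows indicate the maximum severity experienced by each subject at any time point post baseline, including unscheduled assessments".

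**The concern.** A subject can pass screening with ungraded values, have a graded value on the Day 1 draw that nobody sees before dosing, and keep it afterwards. The grade tables enter that subject at each later visit where the value persists, and again in the maximum row, just as they enter a subject whose abnormality began after vaccination.

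The trial has no placebo group and is not randomized, so no concurrent rate of background abnormality is available. Each subject's own Day 1 value is the natural reference, and the summaries do not use it at subject level. With 9 subjects per group, a single person changes the displayed rate by 1/9, or 11 percentage points.

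**Working it through.** **1. Can a subject be graded at screening?** Criterion 10 (Protocol Section 5.1.1) against Appendix C:

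| Parameter | Eligible at screening | Grade 1 |
|---|---|---|
| ALT, IU/L | < 47 | 47–105 |
| Creatinine | ≤ ULN | > ULN to 1.7 mg/dL |
| WBC, 10³/UL | 3.80–13.00 | 2.50–3.50; 13.01–15.00 |
| Hemoglobin, female, g/dL | ≥ 11.5 | 11.0–11.49 |
| Hemoglobin, male, g/dL | ≥ 12.6 | 12.0–12.5 |
| Platelets, 10³/UL | 131–415 | 120–130; 416–550 |

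The ranges do not overlap, so no eligible subject is graded on the qualifying values. Except for low WBC (3.51–3.79 is ineligible but ungraded), the limits adjoin with no margin. Ordinary variation can therefore take a subject near a limit into Grade 1 by Day 1.

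**2. What must happen for carry-over?** Three things together: ungraded at screening, graded on Day 1, and still graded after dosing. Let c be the share of subjects meeting all three. The documents give no value for c.

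**3. Does any rule or table remove such a subject?**
- The pre-existing-condition rule looks at screening, when the value was still ungraded.
- The baseline adjustment in Section 8.5 covers blood pressure only.
- The Day 1 row in Tables 59–61 and 67–70 is a group count. One of 9 on Day 1 and one of 9 on Day 8 may be the same person or two people.
- The summary statistics (Tables 65–66 and 75–77) and Figures 21–25 give group values and mean change from baseline, not grades. The plot with shaded graded ranges announced in Protocol Section 10.5.2 does not appear among the SAP figures.
- No shift table is planned.

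**4. Reproduce the plan's own figure.** Protocol Section 10.2 uses P(at least one of n) = 1 − (1 − rate)^n. At 20% and n = 9: 1 − 0.80^9 = 0.866, the stated 87%. The other tabulated rows also reproduce.

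**5. Apply the same formula to c (assumed values).**

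| c | Expected of 45 (45c) | P(at least one of 9) = 1 − (1 − c)^9 |
|---|---|---|
| 1% | 0.45 | 0.086 |
| 2% | 0.90 | 0.166 |
| 5% | 2.25 | 0.370 |
| 10% | 4.5 | 0.613 |

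**6. Effect of one such subject.** A group with no new abnormality moves from 0/9 to 1/9 = 11%. With the Wilson interval that the SAP uses for AE proportions, this is a move from 0–29.9% to 2.0–43.5%. The laboratory grade tables themselves carry no interval.

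**7. Effect on a real rate.** If the true post-dose rate is p and carry-over is independent of it, the counted rate is 1 − (1 − p)(1 − c). For p = 5% this gives:
- c = 2%: 1 − 0.95 × 0.98 = 6.9%
- c = 5%: 1 − 0.95 × 0.95 = 9.75%
- c = 10%: 1 − 0.95 × 0.90 = 14.5%

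The chance of at least one counted subject in 9 becomes 0.475, 0.603 or 0.756, against 0.370 from the true rate alone.

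**The case against.** The strongest reply is that the plan is more coherent than it first appears, and most of that reply stands.

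- **The blood pressure contrast has a reason.** Section 8.5 explains that eligible blood pressures can already fall in Grade 1. Eligible laboratory values cannot (step 1). A reader might infer that the laboratory rule was simply forgotten. The documents do not show that. What remains is the narrower gap between screening and Day 1.
- **The size is unknown.** A reader might take any plausible rate of out-of-range Day 1 values as the size of the problem. That is the wrong quantity: the value must reach an Appendix C grade and also persist, and a value that was normal at screening may be only briefly abnormal.
- **Subject-level data are planned.** Tables 57–58 list abnormal results by subject with time point, severity and relationship, and Listings 13–14 give every result. With 45 subjects, tracing by hand is feasible.
- **Causality is judged separately.** A reader might infer that carried-over grades would be read as a vaccine effect or would trigger halting. Tables 62–64 and 71–74 are restricted to related results, and the laboratory study-halting and dose-escalation criteria require relatedness. The trial tests no hypothesis.
- **The grade tables are not declared to be the endpoint.** They are titled as laboratory results, and SAP Section 9.6 does not say that their counts are the laboratory AE endpoint. The text therefore does not establish that the primary endpoint is inflated.
- **Counting every grade is a defensible cautious choice** in a first-in-human study. Counting only grades above Day 1 would miss worsening within a grade (ALT from 47 to 105 is Grade 1 throughout). It would also miss a Day 1 grade that normalises and returns after a later dose.

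These points limit the consequences. They do not supply a summary that separates new grades from those already present.

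**Conclusion.** The point holds as a reporting gap. The grade tables mix abnormalities first seen on the pre-dose Day 1 draw with those that appear after dosing, and no other planned summary separates them. The number of affected subjects is unknown and probably small, because criterion 10 confines it to values first graded in the window of up to 30 days before dosing. Under the assumed 1–10% carry-over, the chance that a given group contains at least one such subject runs from 9% to 61%. Each one adds 1/9 at the visits where the value persists and in the maximum row. These figures rest on the assumed c and on independence between subjects; step 7 also assumes that carry-over is independent of new events.

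The documents do not support going further, either to a claim that the primary endpoint is biased by a known amount or to replacing the all-grade count.

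**What to change.** In SAP Section 9.6:

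1. Add, for each of the five parameters, a shift table of Day 1 grade by worst post-dose grade, by treatment group. For WBC and platelets, which Appendix C grades in both directions, keep increases and decreases apart.
2. Add a row to Tables 59–61 and 67–70 counting subjects whose worst post-dose grade exceeds their Day 1 grade. In the any-parameter tables (59 and 67), make the comparison within each parameter before combining, so that a Day 1 grade in one parameter does not hide a new grade in another.
3. Keep the existing all-grade and maximum rows as they are, and report the new row beside them. Do not substitute it as the endpoint count.

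The clinical grading and halting rules need no change. Day 1 samples are already collected and the tables already show Day 1 grades, so the cost is a small amount of programming. Label: free improvement.
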